Peanut equivalent will be used for the food challenge at 0 month maintenance food challenge. The challenge will consist of increasing doses of peanut (in the form of peanut equivalent) given every 15 minutes in increasing amounts (Table 5). The other challenge will consist of placebo material given also in increasing doses. The highest dose will be equivalent to approximately 34 peanuts.

- Review Home Symptom Diary: We will review any symptoms experienced while taking the food protein.
- Urine Pregnancy Test: For females of reproductive potential a urine pregnancy test will be performed prior to the food challenge. If the subject is pregnant the food challenge will not be performed and the subject will be dismissed from the study.

Table 5

0 Month Maintenance Phase Double-Blinded Placebo Controlled Food Challenge Protocol		
Dose Number	Approximate Dose Amount (PEANUT PROTEIN)	Cumulative Dose Amount (peanut protein)
1	75 mg	75 mg
2	150 mg	225 mg
3	500 mg	725 mg
4	1000 mg	1725 mg
5	2000 mg	3725 mg
6	3000 mg	6725 mg
7	4000 mg	10725 mg
8	4500 mg	15225 mg
9	5000 mg	20225 mg
10	6000 mg	26225 mg

6.7. End of Study Food Challenge Visits (24 and 25 months after maintenance dose is reached) (approximately 8 hours per visit):

- Amount of blood to be drawn: At both visits, we will draw up to 4-6 tablespoons of blood (based on the subject's weight) for peanut-specific IgE, IgG, and IgG4, cellular immune studies, and basophil histamine release assays
- Allergy Skin Prick Tests (PST): Endpoint dilution skin testing to peanut will be done at the month 24 and month 25 visit.
- Spirometry or Peak Flow: Spirometry will be attempted in all participants. If valid spirometry results are not successfully obtained, the attempt is documented and peak flow measures will be accepted for the entry criteria with results >90% of predicted. For participants that are able to complete spirometry, FEV1 must be greater than 90% predicted on the day of the challenge to participate in the food challenge.
- Targeted History and Physical Exam and Diet History: A brief medical and diet history will be obtained and a focused physical exam will be performed.
- DBPCFC: The subject will come to Texas Children's Hospital in Houston for a Double Blind Placebo Controlled Food Challenge (DBPCFC) to the study protein (peanut) to determine if he or she is still allergic to peanut or can tolerate peanut.

The DBPCFC visit will last approximately 9 hours. The food challenge may be performed in one day or split into two days. The subject will discontinue antihistamines (for example Zyrtec or Claritin) for 7 days before the procedure and must be off oral corticosteroids for one month before the food challenge.

Peanut equivalent will be used for the food challenge. The challenge will consist of increasing doses of peanut (in the form of peanut flour and mixed with juice or baby food) given every 15 minutes in increasing amounts (Table 6). The other challenge will consist of placebo material given also in increasing doses. The highest dose of peanut flour will be equivalent to approximately 34 peanuts.

They will return 4 weeks after the 24 month food challenge for the 25 month food challenge. It will be conducted in the same manner as the 24 month food challenge. During this 4 week interval the subject must avoid peanut in his or her diet and will not take any peanut protein as he or she had been doing previously.

- Review Home Symptom Diary: At the 24 month visit we will review any symptoms experienced while taking the food protein.
- Urine Pregnancy Test: For females of reproductive potential a urine pregnancy test will be performed prior to the food challenge at both the 24 month and 25 month visits. If the subject is pregnant the food challenge will not be performed and the subject will be dismissed from the study.

Table 6.

24 and 25 Month Maintenance Phase Double-Blinded Placebo Controlled Food Challenge Protocol
--

Dose Number	Approximate Dose Weight (PEANUT PROTEIN)	Cumulative Dose Weight (peanut protein)
1	75 mg	75 mg
2	150 mg	225 mg
3	500 mg	725 mg
4	1000 mg	1725 mg
5	2000 mg	3725 mg
6	3000 mg	6725 mg
7	4000 mg	10725 mg
8	4500 mg	15225 mg
9	5000 mg	20225 mg
10	6000 mg	26225 mg

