- Allergy skin prick tests (A small amount of allergen dissolved in solution is placed on the skin, and the skin is scratched allowing the solution to enter the skin. The presence of a wheal indicates sensitivity to the allergen. The subject will experience itching at the site of the procedure if they are sensitized to peanut. The starting concentration will be the standard peanut extract 1:20 wt/vol with serial dilutions of 1:200, 1:2000, 1:20,000, and 1:200,000 wt/vol as well as oat, wheat, positive (histamine) and negative (saline) controls.)
- Demographic information (age, sex, ethnic origin).
- Serum pregnancy test for menstruating females (1/10 tsp of blood)

- Spirometry: Spirometry will be attempted in all participants. If valid spirometry results are not successfully obtained, the attempt is documented and peak flow measures will be accepted for the entry criteria with results >90% of predicted. For participants that are able to complete spirometry, FEV1 must be greater than 90% predicted.
- Peak flow will be determined for the patient.
- Screening visit will occur within 1 month of the DBPCFC.

6.2. *Study Medication/Intervention:*

The product to be used in this study is only peanut flour. Subjects that cannot tolerate the initial low doses of peanut flour will not be enrolled. The peanut flour will be given in small pre-measured soufflé cups containing the amount of peanut flour that needs to be eaten for one dose.

The flour will be received from the University of North Carolina at Chapel Hill Manufacturing Facility (See Letter of Authorization). Lot-to-lot testing will be performed by the manufacturer on each batch of new peanut flour to ensure accuracy of dosing potency. The process involves running an SDS-PAGE gel with the previous lot and the new lot. Densitometric scanning is then performed to compare Ara h 1 levels and Ara h 2 levels. The University of North Carolina at Chapel Hill Manufacturing Facility has defined the acceptable ranges to be less than 30% for Ara h 1 and 20% for Ara h 2. If a lot fails the test, the batch is discarded and a new lot of peanut flour is ordered. The peanut protein will be received by the Center for Cell and Gene Therapy at Baylor College of Medicine (CAGT).

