- DBPCFC: Subjects eligible for the study (peanut-specific immunoglobulin E level greater than 7kU/L AND a positive skin prick test to peanut) will come to Texas Children's Hospital in Houston for a Double Blind Placebo Controlled Food Challenge (DBPCFC) to the study protein to determine if the subject is allergic to peanut. The table below labeled Table 2 details dosing for the initial DBPCFC and also shows the dose at which the subject will start treatment correlating with the dose at which a reaction is noticed.

Table 2. Entry Double-Blinded Placebo Controlled Food Challenge Protocol and Starting Dose of Oral Immunotherapy to be Initiated				
Dose Number	Approximate Dose Weight (PEANUT FLOUR)	Approximate Dose Weight (PEANUT PROTEIN)	Cumulative Dose Weight (peanut protein)	Starting Dose of OIT if Subject Reacts
1	1 mg	0.5 mg	0.5 mg	Ineligible
2	2 mg	1 mg	1.5 mg	Ineligible
3	10 mg	5 mg	6.5 mg	1.8mg
4	30 mg	15 mg	21.5 mg	3.6 mg
5	108 mg	54 mg	75.5 mg	14.4 mg
6	150 mg	75 mg	150.5 mg	28.8 mg
7	200 mg	100 mg	250.5 mg	40 mg
8	500 mg	250 mg	500.5 mg	120 mg
9	1000 mg	500 mg	1000.5 mg	300 mg
10	2000 mg	1000 mg	2000.5 mg	750 mg

The DBPCFC visit will last approximately 9 hours. The food challenge may be performed in one day or split into two days. The subject will discontinue antihistamines (for example Zyrtec or Claritin) for 7 days before the procedure and must be off oral corticosteroids for one month before the food challenge.

A DBPCFC consists of eating both a food to which the subject may be allergic (peanut) and eating a placebo at different times. A placebo is a substance that is similar to the test substance in appearance, smell, and taste. The peanut protein is a flour and will be given mixed with either juice (at lower doses) or with a food like baby food. The placebo is oat flour for peanut DBPCFC and will be given in the same manner.

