The food will be given in a “double-blinded” fashion under observation at Texas Children's Hospital in Houston. During both of the feedings, the food protein to be given during the challenge will start with the equivalent of less than 1/100th of a peanut and progressively larger doses will be given at 15 minute intervals if the subject does not have an allergic reaction to one of the doses. If the subject does have a reaction to one of the doses, the dosing of study protein will be stopped and the allergic reaction will be treated with an antihistamine and/or epinephrine or other emergency medications which may include but is not limited to bronchodilators, oral or injectable steroids, or H2 blockers). Overall, patients with a history of a prior clinical reaction to peanut will be observed for 120 min after ingestion of the last tolerated dose of peanut protein during the DBPCFC. Patients who have not had previous oral exposure to peanut may

demonstrate a delayed immune response, given the lack of prior peanut exposure. Therefore, those subjects will be observed for a longer duration of 150 minutes. (21-24) The highest dose of peanut protein will be equivalent to 4 peanuts. The initial dose of therapy will be determined by the provider and will be slightly lower than the amount at which the subject reacted to during the DBPCFC (Table 2).

6.4. Buildup Visit Weeks 0 – 50 or until highest tolerated dose (maintenance dose) is reached (approximately 3 hours per visit):

- First build-up visit will occur within 1 month of the DBPCFC. If the subject has symptoms with the first home dose in the clinic, the child may return for a lower dose visit up to two times. If he/she cannot tolerate the 1.8mg dose, the subject will be excluded from the trial.
- Amount of blood to be drawn: Every 6 weeks at weeks 6, 12, 18, 24, 30, 36, 42, 48, etc. we will draw up to 4-6 tablespoons of blood (based on the subject's weight) for immune studies, peanut-specific IgE, IgG, and IgG4 and basophil histamine release assays. Blood will not be drawn at the other build-up visits.
- Peak Flow: Peak flow measures will be accepted with results >90% of predicted.
- Allergy Skin Prick Tests: At week 24, endpoint dilution skin testing to peanut will be repeated. The procedure will be performed as described under section 6.1 "Screening Procedures."

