No subject initiating therapy in this trial will be replaced. The stopping rules for individual subjects are as follows:

- Greater than or equal to four missed or 'no-show' appointments and four missed home doses,
- Greater than 4 instances of not having or carrying an unexpired epinephrine injector to appointments
- Anaphylactic reaction listed as a Grade 4 as defined by the World Allergy Organization grading scale for systemic reactions to immunotherapy related to peanut OIT dosing at any stage of the protocol.
- Any participant is diagnosed with eosinophilic esophagitis
- Any participant is diagnosed with moderate to severe asthma based on the NHLBI guidelines
- Any participant needs treatment with greater than medium daily doses of inhaled corticosteroids, as defined by the NHLBI guidelines
- Any participant has an accidental peanut ingestion with anaphylaxis during the time on oral desensitization

Participants may be prematurely terminated from the study if:

- The participant elects to withdraw consent from all future study activities, including follow-up
- The participant is “lost to follow-up” (i.e., no further follow-up is possible because attempts to reestablish contact with the participant have failed)
- The participant dies

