6.12. Follow-up of Discontinued Participants

Participants who prematurely discontinue treatment with study drug will remain in the study until normal termination. Subjects may receive the option of receiving a peanut equivalent if indicated. All willing subjects will be followed for the duration of the study, and continue blood draws for mechanistic studies while on a peanut restricted diet, and be monitored for accidental ingestions and safety parameters.

Procedure	Screening (Visit 1)	Entry Oral Food Challenge (Visit 2)	Buildup Phase Visit #3-28 (Weeks 0-50)	0 month of maintenance phase (Visit 29)	0 Month DBPCFC (Visit 30)	6 months maintenance phase (Visit 31)	12 months maintenance phase (Visit 32)	18 months maintenance phase (Visit 33)	24 months maintenance phase (Visit 34)	25 months maintenance phase (Visit 35)	End of Study Visit (Visit 36)	Unscheduled visits
Medical/Allergy Hx	X											
Spirometry or Peak Flow	X	X	X	X	X	X	X	X	X	X	X	X
Physical Exam	X	X	X	X	X	X	X	X	X	X	X	X
Diet Hx	X	X	X	X	X	X	X	X	X			X
Targeted Hx		X	X	X	X	X	X	X	X	X	X	X
Review Home			X	X	X	X	X	X	X			X
FAQLQ/F AIM											X	
Endpoint titration	X		X ¹	X			X		X	X		
Texas Children's Hospital in Houston OIT Administration			X	X ⁷							X	X
OIT Maintenance				X	X	X	X	X				
Entry Oral Food Challenge (1 gram of peanut protein)		X										
Oral food challenge					X				X	X		

Procedure	Screening (Visit 1)	Entry Oral Food Challenge (Visit 2)	Buildup Phase Visit #3-28 (Weeks 0-50)	0 month of maintenance phase (Visit 29)	0 Month DBPC FC (Visit 30)	6 months maintenance phase (Visit 31)	12 months maintenance phase (Visit 32)	18 months maintenance phase (Visit 33)	24 months maintenance phase (Visit 34)	25 months maintenance phase (Visit 35)	End of Study Visit (Visit 36)	Unscheduled Visit
Blood draw for immune cell studies		X	X ³		X	X	X	X	X	X		
Buccal mucosal scraping for HLA						X ⁸	X ⁸	X ⁸	X ⁸	X ⁸		
Pregnancy test	X ⁴				X ⁵		X ⁵		X ⁵	X ⁵		
Amount of blood to be drawn	1-2 tsp	4 – 6 tbs ⁶	4 – 6 tbs ^{3,6}		4 – 6 tbs ⁶	4 – 6 tbs ⁶	4 – 6 tbs ⁶	4 – 6 tbs ⁶	4 – 6 tbs ⁶	4 – 6 tbs ⁶		
Time required per visit	~3 hour	~9 hours	~3 hours	~3 hours	~9 hours	~1 hours	~1 hours	~1 hours	~9 hours	~9 hours	~3 hours	~3 hours

¹ will be obtained after 24 week build-up

² will check only peanut -specific IgE at the screening visit.

³ will be obtained at week 6, 12, 18, 24, 30, 36, 42, 48 of build-up phase only.

⁴Beta HCG serum pregnancy test

⁵ Urine pregnancy test

⁶Maximum amount of blood drawn (4 mL/kg)

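### Section 6.4 excludes a child who fails the 1.8 mg dose, 6.12 keeps children who stop treatment in the study, and 9.2.1 names no denominator, so early failures could be left out of the tolerance and symptom rates

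*Combined protocol and SAP*

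**What the plan says.** Section 6.4 covers build-up dosing. Its first visit is tied to the entry challenge: "First build-up visit will occur within 1 month of the DBPCFC". On a reaction to the first dose it sets a limit of two step-down visits ("If the subject has symptoms with the first home dose in the clinic, the child may return for a lower dose visit up to two"), and it then adds: "If he/she cannot tolerate the 1.8mg dose, the subject will be excluded from the trial". In Table 3, 1.8 mg of protein is OIT dose number 1.

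Section 6.12 deals with children who stop treatment: "Participants who prematurely discontinue treatment with study drug will remain in the study until normal termination". It adds "All willing subjects will be followed for the duration of the study", with safety monitoring.

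Two other places touch the same children. Section 6.2 says "Subjects that cannot tolerate the initial low doses of peanut flour will not be enrolled" without saying whether challenge doses or OIT doses are meant. Section 6.11 says "No subject initiating therapy in this trial will be replaced", and its list of individual stopping rules does not include failure at 1.8 mg.

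Section 9.2.1 measures the primary objective by daily symptoms and by the proportion symptom-free at the 6 g challenge, using McNemar's test and exact binomial intervals. Neither 9.2.1 nor section 10 says which children form the denominator, or how a child who stops at the first doses is counted.

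**The concern.** A child who fails the 1.8 mg dose has already consented, gone through the entry challenge and taken study product. Failing to tolerate that product is an outcome of the study. A rule that takes the child out of the trial at that moment selects on the outcome, and nothing in the analysis section puts the child back.

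Safety of the therapy is the stated primary outcome (section 1), and the tolerance proportion is part of the primary objective (2.1.1). If early failures are left out, both results describe only children who tolerated the first doses. With a target of 15 children, one or two omissions are visible in the estimate.

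**Working it through.** **1. Which rule applies to a child who fails 1.8 mg?**

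| Place | What it does with the child |
|---|---|
| 6.4 | Excluded from the trial |
| 6.12 | Stays in after stopping study drug; followed if willing |
| 6.11 | Not replaced; says nothing about staying in or leaving |
| 6.2 | Not enrolled, if OIT doses are meant; silent if challenge doses are meant |

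Table 2 takes the OIT starting dose from the challenge result (column "Starting Dose of OIT if Subject Reacts"), so the first OIT dose comes after the challenge. The child in 6.4 has therefore begun study drug and then stopped it, which is the situation that 6.12 describes. The firm conflict is between 6.4 and 6.12.

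**2. Does the analysis section resolve it?** No. It names the test and the interval method but no population.

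**3. Effect on the tolerance proportion.** The plan gives no expected tolerance rate and no early-failure rate, so there is no figure of its own to reproduce here. Its one sample-size calculation concerns T cells producing interferon-gamma and does not bear on this point.

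Inputs: N = 15 starters (target in sections 1 and 10.1, assuming all 15 take OIT); x = number passing the challenge (assumed 8, 10 or 11); k = early failures left out (assumed 1 or 2).

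Formulas: with all starters counted, x/15; with early failures left out, x/(15 − k). Exact 95% limits are the 0.025 quantile of Beta(x, n − x + 1) and the 0.975 quantile of Beta(x + 1, n − x).

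| x | All 15 | k = 1 | k = 2 |
|---|---|---|---|
| 8 | 53.3% (26.6–78.7) | 57.1% (28.9–82.3) | 61.5% (31.6–86.1) |
| 10 | 66.7% (38.4–88.2) | 71.4% (41.9–91.6) | 76.9% (46.2–95.0) |
| 11 | 73.3% (44.9–92.2) | 78.6% (49.2–95.3) | 84.6% (54.6–98.1) |

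At x = 10 the rise is 71.4 − 66.7 = about 5 points for one child and 76.9 − 66.7 = about 10 points for two.

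**4. Effect on reaction rates.** Let r of the remaining 15 − k children react, and let all k early failures have reacted. Counting everyone gives (r + k)/15; leaving them out gives r/(15 − k). Cross-multiplying, (r + k)(15 − k) − 15r = k(15 − r − k). This is positive unless every child reacted, so leaving them out lowers the rate in every other case. The share failing at the first dose would read 0 instead of 1/15 = 6.7% (0.2–31.9) or 2/15 = 13.3% (1.7–40.5).

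**5. Effect on McNemar's test.** Entry requires a reaction to peanut, so no child is taken as tolerant at baseline. An early failure counted as not tolerant is negative at both times, which is a concordant pair. With x = 10 discordant pairs, all in one direction, the exact p-value is 2 × 0.5^10 = 0.00195 whether early failures are in or out.

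**6. Step-down gap in 6.4.** A child starting at 1.8 mg has no lower Table 3 dose to return for. For higher starting doses, 6.4 allows two lower-dose visits and excludes only on failure at 1.8 mg, but does not fix the size of a step. If each step were one row of Table 3 (an assumption), two steps below 14.4 mg (dose 4) would reach 3.6 mg (dose 2). The six Table 2 starting doses from 14.4 mg upward would then end above 1.8 mg with no stated outcome.

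**The case against.** The strongest reply is that the plan never says these children leave the results, and on safety events its text points the other way. Section 12.5 requires every adverse event to be recorded whatever its perceived cause. Section 12.1 covers events during treatment and throughout the study. The study stopping rules (6.10) count Grade 4 reactions to OIT dosing at any stage, and count repeat epinephrine during escalation or maintenance. This stands. A reader might infer that first-dose reactions vanish from safety reporting or from the stopping counts; the documents do not support that. What remains is that recording an event does not define the denominator of a rate, and 9.2.1 is silent.

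Second, a reader might take the 6.2 sentence as denying enrolment to children already on OIT. It appears under study medication, so that reading is possible. But Table 2 marks a reaction at challenge doses 1 and 2 (1 mg and 2 mg of flour) as ineligible, and on that reading 6.2 is ordinary screening. The sentence is ambiguous and cannot carry the point. Nor can 6.11 be read as keeping such children in, since it only bars replacement.

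Third, failures at 1.8 mg may be few. The 47% with allergic side effects after an initial dose of 6 mg (section 1) counts any side effect in earlier studies and is not a rate of final failure. Here a child has passed challenge doses 1 and 2 without reacting and may step down before exclusion. This stands too: one omission moves 67% to 71%, well inside an interval of 38 to 88.

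**Conclusion.** The point holds as a conflict between 6.4 and 6.12, combined with a missing analysis population in 9.2.1. Because the exclusion is triggered by failure to tolerate study dosing, leaving these children out would bias the estimated tolerance proportion upward and reaction rates downward. In the illustration with 10 passing, the proportion rises by about 5 points for one child and about 10 for two. Those sizes rest on assumed counts and on 15 starters. The direction does not, provided that early failures are counted as not tolerant and that not every child reacts.

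The omission is a possibility left open by the text. It is not something that the plan prescribes, and the McNemar result would be the same either way. The step-down gap is real for a child starting at 1.8 mg. How many higher starting doses it touches cannot be settled, because 6.4 states no step size.

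**What to change.** - **6.4 and 6.12:** reconcile them so that a child who has taken any OIT dose and cannot continue is recorded as a treatment discontinuation and, if willing, followed under 6.12.
- **9.2.1:** state that the population for safety summaries and for the primary tolerance proportion is every child who took at least one OIT dose, and that a child stopped at the first doses counts as not tolerating the challenge.
- **6.2:** say whether the sentence refers to the entry-challenge doses marked ineligible in Table 2. Report children ineligible at the challenge separately, as screening failures.
- **6.4:** reconcile the limit of two lower-dose visits with the exclusion at 1.8 mg, so that every Table 2 starting dose has a defined outcome. The clinical rule is for the sponsor to decide.

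The cost is a few sentences across these sections, plus the follow-up that 6.12 already provides for. The tolerance percentage may come out slightly lower and the reaction rates slightly higher.

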The CAGT is a Good Manufacturing Practice (GMP) compliant facility (See Letter of Authorization) and is accredited by the Foundation for the Accreditation of Cellular Therapy (FACT), the College of American Pathologists (CAP) and is CLIA registered. The protein doses will be monitored and dispensed by the CAGT GMP Facility.

The drug would be stored in the cold room (2-8°C) within the clean room area restricted to CAGT GMP Facility Staff. It is on continuous temperature monitoring via our Isensix system. In the case of an alarm staff is informed via pager system. Alarms and monitoring data are also full backed up by Isensix in San Diego. This drug will be stored in a dedicated facility away from other allergens and will be handled in a separate room on a separate air handling systems.

The pre-measured soufflé cups will be transported by a clinical research staff member within Texas Children's Hospital controlled environment.

The peanut flour will be used within the manufacturer's expiry date and our center will follow all instructions provided by the manufacturer.

One dose of peanut flour is taken per day. Prior to taking the dose the subject must eat a snack high in carbohydrate and fat such as a bagel or chips and then eat the peanut flour mixed into liquid or another food such as apple sauce or ice cream.

The vehicle food for each subject will be a food, to which the subject is not allergic. The subject will need to eat the peanut flour at approximately the same time every day. After eating the peanut flour the subject will need to be with a supervising adult for the next 2 hours so they can monitor for any possible reaction. The subject cannot go to school within 2 hours of eating the

peanut flour and cannot go to bed within 2 hours of eating the peanut flour. After 1 month, if there are no adverse events with the maintenance dose or highest dose tolerated, the provider will have the option of decreasing the observation period to 1 hour with no physical activity to occur for 1 hour.

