- Targeted History and Physical Exam and Diet History: A brief medical and diet history will be obtained and a focused physical exam will be performed.
- Review Home Symptom Diary: At each visit we will review any symptoms experienced while taking the food protein.
- Epinephrine injector will be checked for expiration date and parents/guardian will demonstrate proper use.
- Dose Escalation: The subject must return in no less than 10 days after each visit to receive an increased amount of peanut protein. (See Table 3.) At each visit the subject will be given a slightly larger amount of peanut protein than he or she was receiving prior to that visit. After the first visit the subject will be taking at least the equivalent of approximately 1/100th of a peanut daily and once the subject gets to the maintenance dose he or she will be taking the equivalent of approximately 15 peanuts daily. The length of time the participant is in the build-up phase is dependent on the starting dose determined from DBPCFC and how well each subsequent buildup dose is tolerated. The subject will build up to 3.9 grams of peanut protein or the highest dose tolerated. This is known as the maintenance dose.

Table 3. Dose Escalation Table

Weeks On OIT	Dose No.	Protein Per Soufflé portion cup (mg)	PN flour weight per soufflé portion cup (mg)
0,1	1	1.8	3.6
2,3	2	3.6	7.2
4,5	3	7.2	14.4
6,7	4	14.4	28.8
8,9	5	28.8	57.6
10,11	6	40	80
12,13	7	60	120
14,15	8	80	160
16,17	9	100	200
18,19	10	120	240
20,21	11	240	480
22,23	12	300	600
24,25	13	450	900
26,27	14	600	1200
28,29	15	750	1500
30,31	16	900	1800
32,33	17	1050	2100
34,35	18	1200	2400
36,37	19	1350	2700
38,39	20	1500	3000
40,41	21	1800	3600
42,43	22	2100	4200
44,45	23	2400	4800
46,47	24	3000	6000
48,49	25	3600	7200
50,51	26	3900	7800

6.5. Follow-up Visits (every 6 months for 24 months after maintenance dose is reached) (approximately 3 hour per visit):

Once the maintenance dose is achieved, the patient will follow up in the clinic 2 weeks later to ensure the higher dose is being tolerated and will switch to a peanut equivalent

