dose (Table 4). The first dose of the peanut equivalent will be given in the hospital setting. The family will be instructed on how to administer peanut equivalent dose. The subject will continue to follow the “Instructions for Daily Home Doses” as used for peanut flour dosing. This will be considered “Month 0”. The participant will remain on this dose for 24 months and follow-up visits will occur every 6 months. The subject will continue to follow the peanut flour dosing guidelines. A food challenge will be performed within 1 month of the “Month 0” visit.

Table 4. Peanut Equivalent Dose

Peanut Product	Peanut Protein (gram) /serving	Maintenance Dose (3900mg peanut protein)	Alternative Dose (if maintaining below 3900mg)
Creamy Peanut Butter *Peter Pan or Reese’s Creamy Peanut Butter*	8 grams=2 Tablespoons	1 Tablespoon	1300 mg =1 teaspoon 325mg=0.25 teaspoon
JIF Peanut Powder	8 grams=3 Tablespoons	1.5 Tablespoons	
PB2 Powdered Peanut Butter (Bell Plantation)	5 grams=2 Tablespoons	1.5 Tablespoons	1300 mg= 1.5 teaspoon 300 mg = 3/8ths of a teaspoon
Dry Roasted Peanuts	0.175 grams=1 peanut	22 peanuts	1300 mg = 7 and ½ peanuts 350 mg = 2 peanuts
Peanut M&M’s	0.15 grams=1 piece	26 pieces	1300 mg = 8 and 2/3 pieces 300 mg=2 pieces
Reese’s Pieces Candy	0.078 grams=1 piece	50 pieces	1300 mg = 16 and 2/3 pieces 312 mg = 4 pieces
Reese’s Peanut Butter Cups Miniatures	0.8 grams=1 miniature cup	~5 miniature cups	1300 mg = 1 and 5/8 th cups 300 mg = 3/8 th cup

Other approved alternative:			
-----------------------------	--	--	--

- If the subject experiences no adverse events with the maintenance dose or highest dose tolerated after 1 month, the provider will have the option of decreasing the observation period at home to 1 hour. The subject will need to avoid any form of physical activity 2 hours after ingestion.
- Peak Flow: Peak flow measures will be accepted with results >90% of predicted.
- Amount of blood to be drawn: After maximum tolerated dose is achieved at approximately 1 year (drawn at Visit 30- Month 0 DBPCFC) and every 6 months afterwards, we will draw up to 4-6 tablespoons of blood (based on the subject's weight) for peanut-specific IgE, IgG, and IgG4, cellular immune studies and basophil histamine release assays until the end of the protocol.
- Allergy Skin Prick Tests (PST): Endpoint dilution skin testing to peanut will be done at month 0 and month 12 visits.

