Appendix VIII

Peanut Equivalent Instructions for Daily Home Doses

Subject ID: _____ Date: / / _____

Important: We require that you please carry with you 2 epinephrine auto-injector devices at all times and must demonstrate to the investigators the correct use of the epinephrine auto-injector. Failure to consistently carry an epinephrine auto-injector constitutes grounds for termination from the study. If you do not have an epinephrine auto-injector on your person, your appointment(s) will be rescheduled.

- Take one dose per day, preferably at the same time every day. Prior to taking the dose, you must eat a snack high in carbohydrate and fat (example: bagel, chips) then eat the peanut equivalent based on the “Peanut Equivalent Dosing Guide”.
- After eating the peanut equivalent, your child must be with a supervising adult for the next 1-2 hours (depending on provider’s instructions) so they can monitor for any possible reaction. Your child cannot go to school and cannot go to bed within the observation period. The provider may have the option of decreasing the observation period to 1 hour after 30 days of tolerating the peanut equivalent. Your child may eat and go to school after 1 hour. Your child should continue to avoid physical activity, hot showers, and going to bed within 2 hours of taking the dose.
- Travel
 - International Traveling
 - May consider international traveling once the subject is stable on maintenance for 6 months
 - Try to keep the dosing time period the same as in the USA. Keep the dosing time the same as your place of origin (i.e. dose time in the USA 4pm, then take the dose at 4pm final destination time). Up to 48 hours of dose could be missed
 - No dose should be taken during travel on the plane. Dosing may resume once you arrive at your final destination
 - Domestic Traveling within the continental U.S.
 - Take dose at the same time as place of origin (i.e. dose time in Houston 4pm, then take the dose at 4pm final destination)
 - No traveling on cruise ships

- Please ensure that the peanut equivalent food is not a food that your child is allergic to. Also, be sure to read the label on the food.
- Fill out symptom diary every day and record any symptoms occurring within the observation period of taking the daily dose.

Symptoms to look for:
Mild Symptoms (itching, mild flushing, sneezing, nasal congestion, eye itching, swelling of lips, hives/swelling in one or two areas of the body, nausea)

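### Once home observation is cut to 1 hour, section 6.2 bars physical activity for only 1 hour, while section 6.5 and Appendix VIII bar it for 2 hours; one clause in 6.2 needs correcting.

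*Combined protocol and SAP*

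**What the plan says.** Three places in the combined protocol and SAP set an activity limit for children whose home observation has been shortened to 1 hour.

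- **Section 6.2 (Study Medication/Intervention).** The condition is "After 1 month, if there are no adverse events with the maintenance dose or highest dose tolerated". The provider then has "the option of decreasing the observation period to 1 hour with no physical activity to occur for 1 hour".
- **Section 6.5 (Follow-up Visits).** On the same condition, "the provider will have the option of decreasing the observation period at home to 1 hour". The activity rule follows directly: "The subject will need to avoid any form of physical activity 2 hours after ingestion".
- **Appendix VIII (peanut-equivalent instructions for home doses).** "The provider may have the option of decreasing the observation period to 1 hour after 30 days of tolerating the peanut equivalent". The child may eat and go to school after 1 hour, but "Your child should continue to avoid physical activity, hot showers, and going to bed within 2 hours of taking the dose".

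On timing, section 6.5 says that once the maintenance dose is reached "the patient will follow up in the clinic 2 weeks later to ensure the higher dose is being tolerated", and the switch to peanut equivalent takes place at that visit. It adds: "The subject will continue to follow the peanut flour dosing guidelines".

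**The concern.** The same relaxation, at the provider's discretion, carries two different activity limits. This is an instruction about what a child aged 5 to 16 may do after a home dose of up to 3900 mg of peanut protein, in a phase when scheduled visits are 6 months apart. A provider who consulted section 6.2 alone could let a child be active between 1 and 2 hours after the dose, which section 6.5 and Appendix VIII rule out. The quality assurance review in section 8.3 checks adherence to the treatment as the protocol defines it, and on this point the protocol defines it in two ways.

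Nothing statistical is at stake. The point would fall away if the two limits applied to different children, or if section 6.2 no longer applied in maintenance.

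**Working it through.** The plan gives no figure to reproduce. The check is a comparison of texts, plus a short timing calculation to see whether they cover the same children.

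**Step 1: the texts side by side**

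| Text | When the option opens | Observation | No activity for |
|---|---|---|---|
| Section 6.2 | 1 month without adverse events on the maintenance or highest tolerated dose | 1 hour | 1 hour |
| Section 6.5 | same as 6.2 | 1 hour | 2 hours |
| Appendix VIII | 30 days tolerating peanut equivalent | 1 hour | 2 hours |

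Gap: 2 h − 1 h = 1 h per dose, from minute 60 to minute 120. Two of the three texts say 2 hours. Sections 6.2 and 6.5 share both the condition and the observation period, so the activity limit is the only thing that differs between them.

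**Step 2: does flour versus peanut equivalent explain it?** Take day 0 as the day the maintenance dose is reached. Section 6.4 defines that dose as 3.9 g of peanut protein or the highest dose tolerated, so both groups are covered.

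- Switch to peanut equivalent: 2 weeks = day 14.
- Option opens under sections 6.2 and 6.5: 1 month, taken here as 28 to 31 days (an assumption). The child has then had 28 − 14 = 14 to 31 − 14 = 17 days on peanut equivalent.
- Option opens under Appendix VIII: 14 + 30 = day 44.

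On either count the option opens after the switch. The introduction to section 6 and section 6.2 itself place the switch at the point where the dose is reached, which is no later. If the schedule is followed, every eligible child is already on peanut equivalent, and the 1-hour and 2-hour limits apply to the same children. The two start counts are used only for this check.

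**Step 3: does section 6.2 lapse in maintenance?** No. Sections 6.2 and 6.5 both say that the flour dosing guidelines carry on, and no text says that section 6.5 overrides section 6.2.

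**Step 4: which value fits the rest of the plan?** Appendix VIII separates the two limits on purpose: observation and school may relax to 1 hour, while the activity limit stays at 2. Section 6.5 has the same structure. Section 6.2 is the only text that lets the activity limit shrink along with observation.

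**The case against.** The strongest reply is that the texts closest to practice are already right. The option exists only in maintenance, section 6.5 is the maintenance section, and the family's sheet, which has signature lines for parent and investigator, says 2 hours. Section 6.2 is a general product section written around flour. Its clause also sets a minimum and does not say that activity may resume at 1 hour, so a provider who keeps to 2 hours complies with all three texts. Harm would need someone to read section 6.2 alone and depart from the signed sheet.

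This stands as a limit on the consequence. It does not remove the inconsistency: the 1-hour limit is written as the condition attached to the option, and a reader of that section would take it as the rule.

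A second reply is that Appendix III may need attention too. It bars only strenuous activity, and only during the observation period, and section 6.5 and Appendix VII refer maintenance families to home-dose instructions that could mean Appendix III or Appendix VIII. Appendix III fixes its own observation period at 2 hours, so it does not contradict the correction. Stating 2 hours there would be an optional tidy-up.

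A third reply is that the documents give no rationale for either interval, so the direction of the correction is inferred. That is true. The inference rests on two of three texts, the deliberate wording of Appendix VIII, and caution.

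**Conclusion.** The concern holds. For the same option, open to the same children, section 6.2 sets a 1-hour activity limit where section 6.5 and Appendix VIII set 2 hours. The gap is 1 hour per home dose, only for children whose provider shortens observation. The documents allow no estimate of any effect on reaction rates. This is an internal inconsistency in one clause of a safety instruction: it should be corrected because it concerns children and the remedy is nearly free, but its practical weight is small.

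The conclusion rests on the schedule being followed, so that the switch precedes the option, and on reading 1 month as 28 to 31 days. Any reading longer than 14 days gives the same answer.

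**What to change.** In section 6.2, change the end of the clause so that the shortened observation period comes with *no physical activity of any form for 2 hours after ingestion*. Sections 6.2 and 6.5 and Appendix VIII then agree.

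The cost is one clause. No handout has to be changed or re-issued, and no new data are collected.
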